5.3 Exploratory objectives

Exploratory objective 1:

To determine whether any confirmed positive ADA samples have functional activity that impacts the neutralizing activity of VRC01.23LS, PGT121.414.LS and PGDM1400LS.

Exploratory objective 2:

To further evaluate non-neutralizing antiviral activities, additional assays (eg, antibody-dependent cell-mediated cytotoxicity [ADCC], antibody-dependent cellular phagocytosis [ADCP], virion capture, Fc receptor binding) may be performed for activities that the VRC01.23LS, PGT121.414.LS, and PGDM1400LS are shown to exhibit in vitro

Exploratory objective 3:

To conduct analyses related to predicting serum neutralization over time against a set of potentially exposing viruses in a future efficacy trial for ranking and down-selecting bnAb regimens

Exploratory objective 4:

To conduct analyses related to furthering the understanding of HIV, passive immunity, immunology, Ab mediated prevention, acceptability and clinical trial conduct.

6 Statistical considerations

6.1.1 Sample-size calculations for safety

Primary objective 1 of this study is to evaluate the safety and tolerability of infusion of VRC01.23LS alone, and consecutive IV infusions of VRC01.23LS, PGT121.414.LS, and PGDM1400LS. The goal of the safety evaluation is to identify safety concerns associated with product administration. The ability of the study to detect SAEs can be expressed by the true event rate, defined as the proportion of participants experiencing any SAE, above which at least 1 SAE would likely be observed and the true event rate below which no events would likely be observed. To be more specific, for each treatment group of size n = 5 in Part A, there is a 90% or more chance of observing at least 1 event if the true rate of such an event is 36.9% or more, and there is a 90% or more of observing at least 1 event if the true rate is 2.1% or less. For IV infusion Groups 1-3 combined with n = 15 in Part A, there is a 90% chance or more of observing at least 1 event if the true rate is 14.2% or more, and there is a 90% chance or more of observing at least 1 event if the true rate is 0.7% or less. For each group of size n = 8 in Part B, there is a 90% or more chance of observing at least 1 event if the true

rate of such an event is 25.0% or more, and there is a 90% or more chance of observing no events if the true rate is 1.3% or less. For Group 8 in Part B with n = 30, there is a 90% or more chance of observing at least 1 event if the true rate of such an event is 7.4% or more, and there is a 90% or more chance of observing no events if the true rate is 0.4% or less. Table 6-1 summarizes the probability of observing 0 events, 1 or more events, and 2 or more events among groups of size 5 (Groups 1-3), 15 (Groups 1-3 combined), 8 (Groups 4-7), and 30 (Group 8) for various true event rates. To put these numbers into perspective, in HVTN vaccine trials from December 2000 through April 2014, about 4% of participants who received placebos experienced an SAE.

Group size	True event rate (%)	Pr(0/n1)	Pr(1+/n ₁)	Pr(2+/n1)
	1	0.95	0.05	< 0.01
	4	0.82	0.18	0.01
5	10	0.59	0.41	0.08
	20	0.33	0.67	0.26
	30	0.17	0.83	0.47
	1	0.86	0.14	< 0.01
	4	0.54	0.46	0.12
15	10	0.21	0.79	0.45
	20	0.04	0.96	0.83
	30	< 0.01	> 0.99	0.96
	1	0.92	0.08	< 0.01
8	4	0.72	0.28	0.04
	10	0.43	0.57	0.19
	20	0.17	0.83	0.50
	30	0.06	0.94	0.75
	1	0.74	0.26	0.04
	4	0.29	0.71	0.34
30	10	0.04	0.96	0.82
	20	< 0.01	> 0.99	0.99
	30	< 0.01	> 0.99	> 0.99

Table 6-1 Probability of observing 0 events, 1 or more events, and 2 or more events, among groups of size 5 (Groups 1-3), 15 (Groups 1-3 combined), 8 (Groups 4-7), and 30 (Group 8) for various true event rates

6.1.2 Sample-size calculations for serum mAb concentrations

Primary objective 2 of this study is to evaluate serum concentrations of VRC01.23LS at several timepoints (ie, PK) when administered alone and of VRC01.23LS, PGT121.414.LS, and PGDM1400LS following consecutive IV administration of these mAbs. This objective is descriptive and will be accomplished by estimating the mean serum concentration of each mAb within each treatment group at specific timepoints following each administration. The precision with which a true mean concentration can be estimated from observed data depends on the standard deviation (SD) of the measurements and the sample size. Table 6-2 summarizes two-sided 95% CIs for the mean mAb concentration

for selected values of the observed average mAb concentration and two choices of SDs (SD of log-transformed mAb concentration = 0.5 or 1.0). The construction of these CIs assumed sample sizes of n = 6 or 7 per arm in Groups 4-7 and n = 24 or 27 in Group 8 of Part B, reflecting a missingness rate of 10-20%, compared to a planned treatment group size of 8 participants in Groups 4-7 and 30 participants in Group 8. The calculations assumed that log-transformed serum concentrations are approximately normally distributed. To account for the small sample sizes, a t-distribution was used to construct CIs. For instance, with an observed mean loge serum level of log_e(10 mcg/mL) and assuming an SD of 0.5 for their log-transformed values, a two-sided 95% CI for the true mean mAb concentration level is (5.9, 16.9) (in mcg/mL) with an effective sample size of 6 participants. Of note, an SD of less than 1.0 was generally observed in the log-transformed serum concentrations of VRC01 at various timepoints post–IV infusions of VRC01 in HVTN 104 (57).

Table 6-2 Two-sided 95% CIs based on observing a particular average \log_{e} mAb concentration in Part B participants, taking 10% or 20% attrition into consideration (n = 6/arm or 7/arm for Groups 4-7 and n = 24 or 27 for Group 8 in Part B)

Observed average log _e - mAb concentration (log _e mcg/mL)	SD of log _e - mAb concentration (log _e mcg/mL)	95% CI (mcg/mL) n = 6	95% CI (mcg/mL) n = 7	95% CI (mcg/mL) n = 24	95% CI (mcg/mL) n = 27
$log_e(1)$		(0.59,1.7)	(0.63,1.6)	(0.81,1.2)	(0.82,1.2)
log _e (10)		(5.9,17)	(6.3,16)	(8.1,12)	(8.2,12)
$\log_{e}(50)$	0.5	(30,85)	(31,79)	(40,62)	(41,61)
$\log_{e}(100)$	0.5	(59,169)	(63,159)	(81, 124)	(82,122)
log _e (500)		(296,845)	(315,794)	(405,618)	(410,609)
log _e (1000)		(592,1690)	(630,1588)	(810,1235)	(821,1219)
$log_e(1)$		(0.35,2.9)	(0.40,2.5)	(0.66,1.5)	(0.67,1.5)
log _e (10)		(3.5,29)	(4.0,25)	(6.6,15)	(6.7,15)
$\log_{e}(50)$	1.0	(18,143)	(20,126)	(33,76)	(34,74)
$\log_{e}(100)$		(35, 286)	(40,252)	(66,153)	(67,149)
$\log_{e}(500)$		(175,1428)	(198,1261)	(328,763)	(337,743)
$\log_{e}(1000)$		(350,2856)	(397,2521)	(656,1525)	(673,1485)

6.1.3 Sample-size calculations for serum neutralization activity

Primary objective 3 of this study is to evaluate serum neutralization titers of VRC01.23LS against Env-pseudotyped viruses specific to VRC01.23LS at several timepoints following IV administration of VRC01.23LS and of VRC01.23LS, PGT121.414.LS, and PGDM1400LS against Env-pseudotyped viruses specific to each mAb at several timepoints following consecutive IV administrations. This objective is also descriptive, and will be accomplished by estimating the mean serum neutralization titers of each mAb against the specific virus within each treatment group. The precision with which a true mean neutralization titer can be estimated from observed data depends on the SD of the measurements and the sample size. Table 6-3 summarizes two-sided 95% CIs for

the mean neutralization titer for selected values of the observed average infectious dose ID50 or ID80 neutralization titer. The construction of these CIs assumed sample sizes of n = 6 or n = 24, reflecting an attrition rate of 20% compared to the planned treatment group size of 8 or 30 participants in Part B, respectively. The calculations assumed that log-transformed neutralization titers are approximately normally distributed. To account for the small sample sizes, a t-distribution was used to construct CIs. For instance, with an observed mean titer of $\log_e(50)$ and assuming an SD of 0.5 for their log-transformed values, a two-sided 95% CI for the true mean neutralization titer is (29.6, 84.5) and (40.5, 61.8) with an effective sample size of 6 or 24 participants. Of note, based on neutralization data against a global panel of 11 pseudoviruses in 6 participants in HVTN 104, an SD of approximately 1.0 was observed in the log-transformed ID50 titers at various timepoints post–IV infusions of VRC01 (57).

Table 6-3 Two-sided 95% CIs based on observing a particular average $log_{e^{-}}$ neutralization titer in n = 6 or n = 24 participants in 1 treatment arm, considering 20% attrition of n = 8 or n = 30 participants

Observed average log _e neutralization titer	SD of log _e neutralization titer	95% CI n = 6	95% CI n = 24
log _e (10)		(5.9,17)	(8.1,12)
$\log_{e}(50)$		(30,85)	(40,62)
log _e (100)	0.5	(59,169)	(81,124)
log _e (500)		(296,845)	(405,618)
log _e (1000)		(592,1690)	(810,1235)
log _e (10)		(3.5,29)	(6.6,15)
$\log_{e}(50)$		(18,143)	(33,76)
log _e (100)	1.0	(35,286)	(66,153)
log _e (500)		(175,1428)	(328,763)
log _e (1000)		(350,2856)	(656,1525)

6.2 Randomization

There will be no randomization for Part A. Group 1 will be enrolled first. Contingent on safety data from Group 1, Group 2 will be enrolled. Contingent on safety data from Group 2, Group 3 will be enrolled. Contingent on data from Part A, Groups 4, 5, 6, 7, and 8 will be randomized in blocks to ensure balance across groups for simultaneous enrollment. Specifically, for the first 7 blocks, participants will be allocated according to a 1:1:1:1:4 ratio; for the last block, participants will be allocated according to a 1:1:1:1:2 ratio. A participant's randomization assignment will be computer generated and provided to the CRS pharmacist through a web-based randomization system.

6.3 Blinding

Participants and CRS staff will be unblinded to participant treatment arm assignments. Laboratory Center (LC) staff will be unblinded to whether a sample is from Part A or Part B, but will remain blinded to treatment assignment within Part A or Part B during sample analysis.

6.4 Statistical analyses

This section describes the final study analyses, unblinded as to treatment arm assignment. All safety data from enrolled participants will be analyzed according to the initial randomization assignment regardless of how many study-product administrations and how much study product they received. In the rare instance that a participant receives the wrong treatment at a specific study-product administration time, the Statistical Analysis Plan (SAP) will address how to analyze the participant's safety data. Analyses of safety data are modified intentto-treat (MITT), in that individuals who are randomized but not enrolled do not contribute data and hence are excluded. Because of the brief length of time between randomization and enrollment-typically no more than 4 working days-very few such individuals are expected. The primary analysis of mAb concentration and antiviral functional activity data are per-protocol (PP), in that only individuals who receive the expected mAb at the expected dose level within the expected visit window contribute data. Secondary analysis will also involve the MITT cohort, and when necessary, account for the actual specimen collection time and the actual time and dose amount of each product administration.

Analyses for primary endpoints will be performed using SAS and R. Additional software may be used to perform noncompartmental PK and population PK analyses (eg, Monolix). All other descriptive and inferential statistical analyses will be performed using SAS, StatXact, or R statistical software.

No formal multiple-comparison adjustments will be employed for multiple primary or secondary endpoints. However, multiplicity adjustments will be made for certain primary or secondary endpoint assays, as discussed below, when the assay endpoint is viewed as a collection of hypotheses (eg, testing multiple pseudoviruses to determine a positive antiviral functional activity response). Unless otherwise noted, all statistical tests will be two-sided and will be considered statistically significant if p < 0.05.

6.4.1 Analysis variables

The analysis variables consist of baseline participant characteristics, safety, mAb concentration, mAb functionality, and ADA for primary- and secondary-objective analyses.

6.4.2 Baseline comparability

Treatment arms will be compared for baseline participant characteristics using descriptive statistics.

6.4.3 Safety/tolerability analysis

Since enrollment is concurrent with receiving the first study-product administration, all participants will have received at least 1 product administration and therefore will provide some safety data.

6.4.3.1 Solicited AEs

The number and percentage of participants experiencing each type of solicited AE sign or symptom (see Section 11.2.2) will be tabulated by severity and treatment arm and the percentages will be displayed graphically by arm. For a given sign or symptom, each participant's solicited AEs will be counted once under the maximum severity for all injection visits. In addition, to the individual types of events, the maximum severity of local pain or tenderness, induration or erythema, and systemic symptoms will be calculated. Kruskal-Wallis tests will be used to test for differences in severity between arms.

6.4.3.2 SAEs and unsolicited AEs

Unsolicited AEs (see Section 11.2.2) will be summarized using Medical Dictionary for Regulatory Activities (MedDRA) System Organ Class and preferred terms. Tables will show by treatment arm the number and percentage of participants experiencing an unsolicited AE within a System Organ Class or within preferred-term category by severity or by relationship to study product. For the calculations in these tables, a participant with multiple unsolicited AEs within a category will be counted once under the maximum severity or the strongest recorded causal relationship to study product. Formal statistical testing comparing arms is not planned since interpretation of differences must rely heavily upon clinical judgment.

A listing of SAEs reported to the DAIDS Regulatory Support Center (RSC) Safety Office will provide details of the events, including severity, relationship to study product, time between onset and last study-product administration, and number of studyproduct administrations received.

6.4.3.3 Local laboratory values

Box plots of local laboratory values will be generated for baseline values and for values measured during the course of the study by treatment arm and visit. Each box plot will show the first quartile, the median, and the third quartile. Outliers (values outside the box plot) will also be plotted. If appropriate, horizontal lines representing boundaries for abnormal values will be plotted.

For each local laboratory measure, summary statistics will be presented by treatment arm and timepoint, as well as changes from baseline for postenrollment values. In addition, the number (percentage) of participants with local laboratory values recorded as meeting Grade 1 AE criteria or above as specified in the DAIDS Table for Grading the Severity of Adult and Pediatric Adverse Events (see Section 9.8) will be tabulated by treatment arm for each post–study-product administration timepoint. Reportable clinical laboratory abnormalities without an associated clinical diagnosis will also be included in the tabulation of AEs described above.

6.4.3.4 Reasons for study-product administration discontinuation and early study termination

The number and percentage of participants who discontinue study-product administration and who terminate the study early will be tabulated by reason and treatment arm.

6.4.4 mAb concentration and PK analysis

6.4.4.1 Primary analyses of mAb concentrations

The primary analysis of serum concentration and PK of VRC01.23LS, PGDM1400LS, and PGT121.414.LS (primary objective 2) will be restricted to participants who received all scheduled administrations PP. Serum concentrations that fail the quality control of the assay, are from specimens collected outside of the visit window, or are from participants with HIV postacquisition may be excluded. The primary analysis of serum concentration will be descriptive and performed separately for each mAb. As an exploratory analysis, we will consider a pooled analysis across different dosing arms and investigate if the PK is modified by the dose. We will also compare the PK of VRC01.23LS administered alone with that of VRC01.23LS administered in combination with PGDM1400LS, and PGT121.414.LS.

A noncompartmental PK analysis will be performed on the concentration data. PK parameters may include, but are not limited to: AUC, Cmax, time to Cmax (Tmax), CL, Vd, terminal elimination rate constant (λz), and the terminal t1/2. Data will be summarized by each dose group and overall for CL, Vd, and t1/2. The potential for nonlinear PK will be determined by comparing the dose-adjusted ratios for Cmax and AUC within dosing groups. Graphical displays of the data (eg, boxplots, scatterplots, histograms, spaghetti plots) will be generated to visually explore distributional properties of the data. These summary statistics and graphical displays may be produced for each treatment arm and each timepoint separately. These summary statistics and PK parameters including half-life, will be compared to the published results of VRC01, VRC01LS, and VRC07-523LS.

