participants will receive 2 doses 6 months apart of VRC01.23LS + PGT121.414.LS + PGDM1400LS administered in combination with weight-based dosing as follows: 5 + 5 + 5 mg/kg IV, 20 + 5 + 5 mg/kg IV, 20 + 20 + 20 mg/kg IV, 40 + 5 + 5 mg/kg IV, and 40 + 40 + 40 mg/kg IV (Groups 4-8). Participants will be followed for 6 months in Part A and 12 months in Part B.

Figure 4-2 Breadth and potency curves for PGT121, PGDM1400, VRC01, VRC01.23LS, and 2 triple combinations (PGT121 + PGDM1400 + VRC01 and PGT121 + PGDM1400 + VRC01.23LS) to a panel of 108 viruses (61 from Clade B and 47 from Clade C) from the placebo arm in the AMP trials.

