5.1 Primary objectives and endpoints

Primary objective 1:

To evaluate the safety and tolerability of VRC01.23LS when administered alone via IV route (Part A) and of VRC01.23LS + PGT121.414.LS + PGDM1400LS, when administered consecutively via IV route (Part B)

Primary endpoints 1:

- Local and systemic solicited AEs, laboratory measures of safety, unsolicited AEs, and SAEs
- Early discontinuation of administration and reason(s) for discontinuation and early study termination

Primary objective 2:

To evaluate the serum concentrations and PK of VRC01.23LS when administered alone via IV (Part A) and of VRC01.23LS + PGT121.414.LS + PGDM1400LS after consecutive administration via IV route (Part B)

Primary endpoint 2:

Serum concentrations of VRC01.23LS, PGT121.414.LS, and PGDM1400LS at prespecified timepoints among participants who received all scheduled product administrations

Primary objective 3:

To evaluate the individual mAb-specific serum neutralizing activity of VRC01.23LS when administered alone via IV route (Part A) and of VRC01.23LS + PGT121.414.LS + PGDM1400LS, after consecutive administration via IV route (Part B)

Primary endpoint 3:

Magnitude of serum neutralizing activity measured with mAb-specific Envpseudotyped viruses in TZM-bl cells at prespecified timepoints among participants who received all scheduled product administrations

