6.4.5 Analysis of neutralization activity and correlation with serum concentrations

6.4.5.1 Primary analyses of neutralization magnitude-breadth (MB) curves

To address primary objective 3, at each specified timepoint, the area under the magnitude-breadth curve (AUC-MB) to a global panel of pseudoviruses (58) will be computed for each participant in the PP cohort with evaluable neutralization ID₅₀ or ID₈₀ data, as described in (59). Magnitude-breadth (MB) curves will be employed to display individual- and group-level response breadth as a function of magnitude. Response breadth is defined as the percentage of viruses in the panel with neutralization titer above certain thresholds. Comparisons of the MB curves among arms will be based on a nonparametric Wilcoxon rank sum test on the participant-specific AUC-MB and a Kolmogorov-Smirnov type test on the group-average MB curves. Simulations will be used to obtain two-sided p-values for the latter test. An alternative approach based on constructing a weighted-average score-like variable will be explored. Details of either approach will be described in the SAP.

6.4.5.2 Secondary analyses of correlations between serum concentrations and serum neutralization levels

To address secondary objective 1, pharmacodynamics (PD) models based on either linear or nonlinear mixed effects models will be performed to characterize the correlation between serum concentration (observed or population pharmacokinetic [popPK] model-predicted) and serum neutralization against each virus or the AUC-MB of serum neutralization against the panel. Data from all enrolled participants will be analyzed regardless of how many administrations and how much mAb dose they received (MITT analysis). Similar to the popPK analysis, data from specimens collected outside of the visit window may be included in the PK/PD analyses that account for the actual specimen collection time and the actual time and dose amount of each product administration. Since the exact date of HIV acquisition is unknown, any serum-level data from blood draws 4 weeks prior to a participant living with HIV's last seronegative sample and thereafter may be excluded. All data from participants living with HIV who have no seronegative samples postenrollment may be excluded from the analysis.

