7.3.2 Participant departure from study-product administration schedule

Every effort should be made to follow the study-product administration schedule per the protocol. If a participant misses a study-product administration and the visit-window period for the study-product administration has passed, that study product cannot be given. The participant should be asked to continue study visits. (see Sections 7.3.1 and 7.3.3).

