7.3.3 Discontinuing study-product administration for a participant

Under certain circumstances, an individual participant's study-product administrations will be permanently discontinued. Specific events that will result in stopping a participant's study-product administration schedule include:

- Coenrollment in a study with an investigational research agent (rare exceptions allowing for the continuation of study-product administrations may be granted with the unanimous consent of the HVTN 143/HPTN 109 PSRT)
- Clinically significant condition (ie, a condition that affects the immune system or for which continued study-product administrations and/or blood draws may pose additional risk), including but not limited to the following:
 - HIV acquisition
 - Any grade 4 local or systemic solicited or unsolicited AE that is subsequently considered to be related to study-product administration
 - Grade 3 clinical AE that is subsequently considered to be related to studyproduct administration with the exception of fever, vomiting, and subjective local and systemic symptoms. For grade 3 infusion-site erythema and/or induration, upon review, the HVTN 143/HPTN 109 PSRT may allow continuation of study-product administration
 - Any grade 3 or 4 lab abnormality confirmed by a repeated value that is subsequently considered to be related to study product;
 - SAE that is subsequently considered to be related to study-product administration

- Clinically significant hypersensitivity or mAb reaction including, but not limited to, type 1 hypersensitivity reaction, urticaria, or serum sickness associated with study-product administration. Consultation with the HVTN 143/HPTN 109 PSRT is required prior to subsequent studyproduct administrations following any hypersensitivity reaction associated with study-product administration
- Investigator determination in consultation with Protocol Team leadership (eg, for repeated nonadherence to study staff instructions)

Participants discontinuing study product for reasons other than HIV acquisition should be counseled on the importance of continuing with the study and strongly encouraged to participate in follow-up visits and protocol-related procedures per the protocol for the remainder of the trial, unless medically contraindicated (see HVTN 143/HPTN 109 SSP).

Participants diagnosed with HIV during the study should be encouraged to participate in follow-up visits as indicated in Section 9.12.

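### Part B first-infusion PK and neutralization results enter the primary analysis only if the participant also received infusion 2 about six months later

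*Protocol*

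**What the plan says.** Section 5.1 defines primary endpoint 2 (serum concentrations) and primary endpoint 3 (neutralization magnitude) "at prespecified timepoints among participants who received all scheduled product administrations". Section 6.4.4.1 repeats the condition for the primary PK analysis, which "will be restricted to participants who received all scheduled administrations PP". For primary objective 3, section 6.4.5.1 has the area under the magnitude-breadth curve "computed for each participant in the PP cohort with evaluable neutralization" data, at each specified timepoint. The general PP definition in section 6.4 is that "only individuals who receive the expected mAb at the expected dose level within the expected visit window contribute data".

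In Part B, "participants will receive 2 doses 6 months apart of VRC01.23LS" and its two partner antibodies (section 4.1.1), on Day 1 and Day 169. Appendix K allows infusion 2 within 14 days either side of Day 169. Section 7.3.2 adds that once the "visit-window period for the study-product administration has passed, that study product cannot be given". Section 7.3.3 lists the reasons for permanent discontinuation, among them HIV acquisition, related SAEs, certain related grade 3 or 4 events, and "Clinically significant hypersensitivity or mAb reaction including, but not limited to, type 1 hypersensitivity reaction, urticaria, or serum sickness".

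On the other set, section 6.4 states: "Secondary analysis will also involve the MITT cohort". The secondary endpoints in section 5.2 cover all participants whatever number of infusions they had.

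**The concern.** The condition applies to the participant, not to the infusion interval. Whether someone belongs in the Day 4 or Day 57 summary depends on what happens around Day 169, after those samples were taken. Three things follow.

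- **Conditioning on a later event.** The first-infusion mean is an estimate for those who went on to a second infusion, not for those correctly given the first. Section 6.1.2 describes objective 2 as estimating means at timepoints after each administration, so first-infusion estimates are a primary target in their own right.
- **Valid data set aside.** Sections 7.3.2 and 7.3.3 ask or encourage participants who miss or stop product to stay in follow-up. Their first-interval samples are collected and then left out of the primary analysis, in four arms of only 8.
- **Asymmetry with Part A.** Part A has one infusion and so no later condition. Section 6.4.4.1 plans to compare VRC01.23LS alone with VRC01.23LS in combination, and section 4.2 hopes to show that coadministration leaves half-life unchanged. One side of that comparison is selected on a Day 169 event and the other is not.

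**Working it through.** **1. Which samples are affected.** Appendix G schedules Part B concentration samples 1 hour after infusion 1 and on Days 4, 7, 29, 57, 113 and 169. Its footnote says stored serum is drawn before product is given, so the Day 169 sample also precedes infusion 2. That makes seven post-infusion-1 concentration samples. Neutralization serum is taken at the same visits from Day 4 to Day 169, which makes six. None depends on infusion 2 having been given.

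**2. Is the condition really on the participant?** Section 6.4 alone could be read timepoint by timepoint. Sections 5.1 and 6.4.4.1 both say all scheduled administrations, and the secondary endpoints drop that condition expressly. Read together, the primary restriction is at participant level. No rule keeps first-interval data from someone who misses infusion 2.

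**3. The plan's own precision figure.** Section 6.1.2 uses m × exp(± t(0.975, n−1) × SD/√n). With m = 10 mcg/mL, SD = 0.5 and n = 6, this gives (5.92, 16.90), which matches the stated (5.9, 16.9). With m = 50 and n = 24 it gives (40.48, 61.75), which matches the (40.5, 61.8) in section 6.1.3. The stated figures are right.

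**4. Chance that an arm of 8 is affected.** The protocol gives no rate p of missed or stopped second infusions, so a range is assumed. P(at least one lost) = 1 − (1 − p)^8, and the expected loss over Part B is 62p (4 × 8 + 30 = 62).

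| Assumed p | P(arm of 8 loses at least 1) | Expected loss of 62 |
|---|---|---|
| 5% | 1 − 0.95^8 = 0.337 | 3.1 |
| 10% | 1 − 0.90^8 = 0.570 | 6.2 |
| 15% | 1 − 0.85^8 = 0.728 | 9.3 |
| 20% | 1 − 0.80^8 = 0.832 | 12.4 |

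**5. What a lost profile costs.** The log-scale half-width is proportional to t(0.975, n−1)/√n: 0.836 at n = 8, 0.925 at n = 7 and 1.049 at n = 6. Going from 8 to 7 or 6 widens the interval by 0.925/0.836 = 1.11 or 1.049/0.836 = 1.25. Table 6-2 already plans on 6 or 7 of 8, so this is precision the trial could keep. It is not a shortfall against the stated plan.

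**6. Conditional bias arithmetic.** If excluded participants' first-interval log concentrations were lower by d, the PP geometric mean would exceed the all-treated one by a factor exp(p × d). For d from 0.25 to 1.0 this is 1.01 to 1.05 at p = 5% and 1.05 to 1.22 at p = 20%. Both p and d are assumptions. The protocol supplies neither, and d could be zero.

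**The case against.** The strongest reply is that nothing is lost to the trial. The excluded data stay in the planned MITT analyses and the secondary endpoints. Secondary objective 3 relates antidrug antibodies (ADA) to concentration directly, and section 6.4.6 foresees further analyses of ADA impact on PK. Objectives 2 and 3 are descriptive, the comparison of VRC01.23LS alone and in combination sits beside an exploratory analysis, and the Part A arms have 5 participants each, so sampling error is large anyway. All of this stands and limits the consequence. It does not justify the rule: the MITT set may also include wrong-dose or out-of-window data, so it is not a clean first-infusion PP estimate.

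Sister-trial counts also suggest few losses. In section 4.4.6, 48 participants given the combination IV had 96 IV infusions (48 × 2 = 96), which points to complete second dosing. In section 4.4.4, 33 administrations compare with 36 implied by the schema (6 + 6 + 6 + 9 × 2), but no participant stopped product because of an AE. This argues against a large AE-driven selection, and it stands.

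It may be said that PP rules belong in the statistical analysis plan. That does not help here, because the condition is written into the endpoint definitions of the protocol itself.

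**Conclusion.** The point holds on the text: the primary PK and neutralization endpoints condition Part B first-infusion results on a second infusion, with no counterpart in Part A. The effect is probably modest. The range of 34% to 83% for an arm of 8 losing at least one profile rests wholly on an assumed 5% to 20% of second infusions missed, taken as independent between participants.

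Three stronger readings are not supported.

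- A reader might take the 10% to 20% missingness in section 6.1.2 as the rate of missed second infusions. Section 6.1 frames its allowance as lab data missing at a given timepoint, from early termination, shipping or assay background.
- A reader might add that full allowance to missed infusions and conclude that Table 6-2 is too optimistic. Early termination is already in the allowance, so this counts part of the loss twice. The protocol does not say whether PP exclusions are included.
- A reader might infer a demonstrated bias, because hypersensitivity or serum sickness could accompany ADA and faster clearance, and because one macaque in section 4.3.1.3 cleared the antibody quickly with ADA held responsible. No abnormal clinical signs were seen in any animal, so nothing reported there would have stopped dosing under section 7.3.3, and no second dose was planned. The protocol shows no link between stopping reasons and clearance in humans.

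**What to change.** Define the PP set by infusion interval. Everyone who correctly received infusion 1 contributes concentrations and titers up to infusion 2, expressly including the Day 169 pre-infusion sample. Only summaries after infusion 2 require that both infusions were correctly received. In sections 5.1 (endpoints 2 and 3), 6.4, 6.4.4.1 and 6.4.5.1, replace the condition with receipt of all administrations scheduled up to that timepoint. The secondary MITT analyses can stay as they are.

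The cost is a wording change. The PP n will differ slightly by timepoint and should be shown in each table. No new visits, samples or participants are needed.
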